9.2.1. Inclusion criteria

All patients from Study C4181005 who have completed Visits 1 through 11 (at D183) will be included in this project.

To construct a concurrent external control, patients from Study C4181001 will need to meet the following inclusion criteria from Study C4181005 to be eligible for inclusion:

- Documented, confirmed genetic diagnosis of achondroplasia from historical medical records (test must have been performed at a laboratory fully accredited for genetic testing under local regulations)
- Aged \geq 3 months to <11 years (up to the day before 11th birthday inclusive) at time of enrollment into the observational natural history study.
- Havecompleted at least 2 valid height/length measurements (at least 3 months apart)
- Assessed for Tanner stage 1 during physical examination before or at enrollment (must include assessment of breast development for females, testicular stage for males)

- Able to stand independently for height measurements (if ≥ 2 years of age at enrollment); If aged <2 years at enrollment, has a documented historical MRI brain/cervical spine performed in the previous 12 months.
- Have at least 6 months of available follow-up data after enrollment into the natural history study

9.2.2. Exclusion criteria

Patients meeting any of the following criteria will not be included in the study:

- Presence of severe obesity (BMI>95% percentile on Hoover-Fong BMI charts);
- Body weight <7kg or >30kg
- History of chronic kidney disease (CKD) or renal impairment
- History of receipt of any treatment that are known to potentially affect growth (including oral steroids > 5 days in the last 6 months before enrollment, high dose inhaled corticosteroids (>800 mcg/day beclametasone equivalent) and medication for attention deficient hyperactivity disorder.
- Less than 6 months since fracture or surgical procedure of any bone determined from the baseline visit date.
- Presence of any internal guided growth plates/devices
- History of removal of internal guided growth plates/devices within 6 months prior to enrollment

9.3. Variables

Table 3. Listing of all variables of importance

Variable	Role	Phase II Recifercept Clinical Trial (C4181005)	Natural History Study (C4181001)	Operational definition
Achondroplasia treatment	Exposure	Recifercept dosage and duration: Recifercept dosage: 1mg/kg once-weekly 2mg/kg twice-weekly 1.5mg/kg once-daily	Achondroplasia-related treatment and duration Collected every 3 months	
Height Growth	Primary outcome	Collected every 3 months until end of study participation	Collected every 3 months until end of study participation	Defined as increase in height growth above expected growth in reference population, defined as the height growth in the achondroplasia reference population +50%
Anthropometric Measurements	Secondary outcome	 Standing height Sitting height Knee height Arm span Length of the legs Sitting height/standing height ratio Arm span to height/length difference knee height: lower segment ratio Collected at 1m, 3m, 6m, 9m, 1y 	 Standing height Sitting height Knee height Arm span Length of the legs Sitting height/standing height ratio Arm span to height/length difference knee height: lower segment ratio -collected at baseline, every 3m, and end of study visit 	Length of the legs will be calculated as the difference between standing and sitting height
Achondroplasia- related orthopaedic complications	Secondary outcome	Baseline collection - foramen magnum decompression - cranial surgery Occurrence during follow-ups	 Lordosis Kyphoscoliosis Small foramen magnum Spinal stenosis collected at 6m, 1y, 2y, 3y, and 4y Collected every 3 months until end of study participation 	

PFIZER CONFIDENTIAL CT24-WI-GL02-RF02 3.0 Non-Interventional Study Protocol Template For Secondary Data Collection Study 23-May-2022 Page 19 of 26

Other achondroplasia- related complications	Secondary outcome	 Sleep disordered breathing Acute Otitis Media (AOM) Hydrocephalus 	 Sleep disordered breathing Acute Otitis Media (AOM) Hydrocephalus 	
CCI				
Demographics	Covariate	- Age	- Age	
		- Gender - Race and ethnicity	- Gender - Race and ethnicity	
		Collected at baseline	Collected at baseline	
Puberty	Covariate	Tanner stage	Tanner stage	
		Collected at baseline	Collected at baseline	
Weight	Covariate	Body weight	Body weight	
		Collected every 3 months until end of	Collected every 3 months until end of	
		study participation	study participation	
History of	Covariate	Sleep-disordered breathing	Sleep-disordered breathing	
achondroplasia-		Chronic otitis media	Chronic otitis media	
related medical		Lordosis	Lordosis	
conditions		Kyphosis	Kyphosis	
		Spinal stenosis	Spinal stenosis	
		Hydrocephalus	Hydrocephalus	
		Assessed at baseline		

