9.2. Setting

This retrospective cohort study will include achondroplasia patients from Study C4181005 and those from Study C4181001 who meet the inclusion and exclusion criteria of Study C4181005. Study C4181005 is a single-arm trial to evaluate the safety and tolerability of recifercept doses and dosing regimen, and efficacy to increase height growth in achondroplasia patients. Study C4181005 will include approximately 63 children with achondroplasia aged 3 months to 10 years (inclusive) with Tanner Stage 1, who are enrolled and randomized to receive one of three doses of recifercept (1mg/kg once-weekly, 2mg/kg twice-weekly, or 1.5mg/kg once-daily) subcutaneously for 12 months. Demographics, medical history, anthropometric measurements, and patient-reported outcomes in functional status and quality of life are collected approximately every 3 months. Study C4181001 is a prospective natural history study to collect the longitudinal anthropometric and diseaserelated complication data in children with achondroplais. It will include approximately 300 achondroplasia patients aged 0-15 years with Tanner Stage I recruited from global sites. Patient data will be collected at baseline and at every 3-month interval visits, for a maximum of 5 years. Further details on data sources are presented in Table 1.

	Recifercept phase 2 Clinical Trial (Study C4181005)	Natural History Study (Study C4181001)
Study population	3m-10y, Tanner Stage 1	0-10y, Tanner Stage 1
Study duration	12 months	Up to 5 years
Visit interval	- Medical history collected at baseline	- Complications collected every 3 months
	- Anthropometric measurements every 3 months	- Anthropometric measures every 3 months
	- Biomarkers baseline, D1, D4, D8, D15, D29, M2, M3, M6, M9, M12	- Biomarkers sample taken once annually
	CCI	
Sample size	63 patients	300 patients anticipated
Primary objective	- Evaluate the safety and tolerability of recifercept doses and dosing regimens in participants aged ≥ 2 to <11 years with achondroplasia	- Collection of longitudinal anthropometric and disease-related complication data in children with achondroplasia

Table 2. Data sources*

PFIZER CONFIDENTIAL

CT24-WI-GL02-RF02 3.0 Non-Interventional Study Protocol Template For Secondary Data Collection Study 23-May-2022 Page 16 of 26

V 1.1, NOV 09, 2025		
	- Assess efficacy of recifercept to increase height growth in children with achondroplasia	

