7.2 STATISTICAL ANALYSES

To evaluate objective 2, mixed-effect, repeated measures (MMRM) models will be used. The fixed effects of treatment, visit, treatment-by-visit interaction, age and gender will be included. Visit will be modeled as a categorical covariate. (If the model does not converge then Visit will be modeled as a continuous covariate.) There will be random effects for both slopes (i.e. visit as a continuous variable) and intercept, clustered by subject nested within a propensity-score matched set or clustered by subject weighted by Inverse Probability Weights (see section 10.3). Random effects for slopes will be removed in the above models do not converge. Unstructured covariance matrix will be assumed for the model errors.

7.2.1 Objective 1

To construct a concurrent external control for Study C4181005, a propensity score (PS) will be created to achieve balance across covariates between achondroplasia patients from Study C4181005 and patients from Study C4181001 who meet all the eligibility criteria of Study C4181005. The PS will be estimated using standard logistic regression approaches with the "outcome" variable being the data source (whether patients were included in Study C4181005 and exposure to recifercept treatment) and the predictors being the variables associated with both the exposure (recifercept treatment) and the outcomes of interest (i.e. standing height & arm-span-to-height difference). This model will provide the predicted probability of being in the trial cohort relative to the concurrent external control cohort as a function of the covariates (the propensity score of being included in Study C4181005). The potential covariates may include demographics (e.g. age, gender, race and ethnicity), clinical characteristics (e.g. presence of achondraplasia-related complications, Tanner stage, and other non-achondroplasia-

PFIZER CONFIDENTIAL

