Another method to construct an external control for C4181005 for the purpose of estimating the Average Treatment Effect (ATE) of recifercept is Inverse Probability Weights (IPW). IPW will use PS to weight the observations prior to the analysis of height growth. Weights are calculated for each subject as 1/PS for Recifercept and 1/(1-PS) for the untreated group. Standardized differences between the untreated and Recifercept groups will be assessed both before and after weighting. Standardized mean differences of <10% may be considered a negligible difference.

7.2.2 Objective 2

Achondroplasia disease measures including height growth, anthropometric measurements, difference in functional status and health-related of life will be summarized using descriptive statistics.

Analyses of Height Z-Score and Arm-Span-to-Height Difference

If objective 1 is met, either a matched dataset – exclusively with a ratio of treated to untreated of 1:1 - via PS or a dataset augmented by IPW will be used to analyze height Z-Score. Baseline summaries of Height Z-score and Arm-Span to Height-difference and change from baseline a months 3, 6, 9, and 12 will be presented.

7.2.3 Safety Analyses

Not applicable.

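### Protocol Table 3 gives the trial a month-1 anthropometry visit that the controls lack; if those heights reach the Objective 2 models, as nothing in the SAP prevents, the coded treatment coefficient can be distorted

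*Protocol*

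**What the plan says.** **Schedule.** In the anthropometric row of Table 3 (protocol 9.3), the trial column reads "Collected at 1m, 3m, 6m, 9m, 1y" and the natural history column reads "collected at baseline, every 3m, and end of study visit". That row covers standing height and arm span, the source measurements for both endpoints in SAP 5.1. Other entries differ for the trial. Protocol Table 2, repeated in SAP Table 1, gives "Anthropometric measurements every 3 months", and the height-growth row of Table 3 gives "Collected every 3 months until end of study participation".

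**Pooling.** Protocol 9.7 and SAP 2.1 say that the listed variables from both studies are pooled into one dataset. They cite a Table 9.3, which appears to mean Table 3 of section 9.3.

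**Text model.** SAP 7.2 says "The fixed effects of treatment, visit, treatment-by-visit interaction, age and gender will be included" and "Visit will be modeled as a categorical covariate", with a fallback: "If the model does not converge then Visit will be modeled as a continuous covariate". It does not list the visits to be modelled.

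**Summaries.** SAP 7.2.2 says that "change from baseline a months 3, 6, 9, and 12 will be presented".

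**Code.** Both model programs in SAP 10.3 fit change on month and drug, with month continuous, no interaction, and a random intercept and slope by subject. The matched program has no WHERE statement. The WHERE line of the weighted program is not fully legible in the extracted text, but shows no condition on visit.

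**The concern.** The comparison depends on the two cohorts being observed at the same times. A time point present in one arm only carries no information on the difference at that time. A model with a single treatment coefficient and a straight line in month still uses it.

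Two consequences follow. If a treatment effect builds up over the year, the treated arm gains an early record at which little effect has appeared, and the single coefficient moves towards zero. If there is no effect but the change in Z-score common to both arms is not linear, the extra early point makes the arms' fitted lines differ, and a non-zero coefficient appears from the schedule alone. Height Z-score is the subject of the only stated hypothesis (SAP 3.1), tested at two-sided 0.05.

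**Working it through.** The plan gives no figure that depends on the visit schedule, so there is nothing of its own to reproduce.

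**Inputs from the documents.** If month 1 exists, treated visits are {1, 3, 6, 9, 12} and control visits {3, 6, 9, 12}. The model forms are those of SAP 7.2 and 10.3.

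**Assumed inputs.** The documents give no variance components, effect shape or common trend. Assumed here: equal arms; independent random intercept and slope; no weighting; and four sets of standard deviations in Z units (intercept, slope per month, residual), shown below.

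**Step 1: text model (categorical visit with interaction).** A contrast is estimable if adding it as a row leaves the rank of the design unchanged. Five treated and four control cells give rank 9.

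| Contrast (treated minus control) | Rank with contrast added | Estimable |
|---|---|---|
| Month 1 | 10 | no |
| Average of all five visits | 10 | no |
| Month 3, 6, 9 or 12, each | 9 | yes |
| Average of months 3, 6, 9, 12 | 9 | yes |

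**Step 2: coded model, effect growing linearly to 0.5 Z at month 12.** The fitted mean is b0 + b1·month + b2·drug. The expected coefficients are (ΣX'V⁻¹X)⁻¹ ΣX'V⁻¹μ, with V = ZGZ' + σ²I and μ = 0.5·t/12 in the treated arm, 0 in controls. The entries are b2.

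| SDs (intercept, slope, residual) | Shared visits only | With treated-only month 1 | Relative loss |
|---|---|---|---|
| 0.15, 0.02, 0.15 | 0.174 | 0.145 | 16% |
| 0.05, 0.03, 0.10 | 0.062 | 0.048 | 23% |
| 0.20, 0.01, 0.20 | 0.281 | 0.256 | 9% |
| 0.10, 0.04, 0.10 | 0.038 | 0.029 | 24% |

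With a constant effect of 0.3 Z, b2 is 0.300 in all four sets, with or without month 1.

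**Step 3: coded model, no effect, curved common trend.** Both arms follow μ = -0.3·√(t/12).

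| SDs | Shared visits only | With treated-only month 1 |
|---|---|---|
| 0.15, 0.02, 0.15 | 0 | +0.014 |
| 0.05, 0.03, 0.10 | 0 | +0.019 |
| 0.20, 0.01, 0.20 | 0 | +0.007 |
| 0.10, 0.04, 0.10 | 0 | +0.020 |

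If the common trend is linear, b2 is 0 in every set, with or without month 1.

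**Step 4: wider assumptions.** With no random slope, month 1 multiplies b2 by 0.94 for a linear effect, or by 0.92 for one that saturates with a 3-month time constant: a loss of 6-8%. Over a wider grid with a random slope (SD 0.02-0.05 per month, one set with intercept-slope correlation -0.3), the factor is 0.75-0.94 for a linear effect and 0.67-0.82 for a saturating one: a loss of 6-33%.

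**The case against.** The strongest reply is that month-1 heights may not exist, or may never reach the model. Only one cell of Table 3 lists them; Protocol Table 2, SAP Table 1, the narrative text and the height-growth row all give roughly 3-monthly measurement. The Day 29 window in SAP A1.1 settles nothing, because that is a general list of visit labels, and Table 2 gives another reason for the visit (biomarkers). The model programs read prepared datasets whose construction is not shown, so the absence of a filter does not prove that month-1 rows are in them. All of this stands, and it makes the point conditional. It does not remove it: the anthropometry row is the more specific entry, the Table 3 data are said to be pooled, and nothing in the SAP excludes the visit.

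A reader might infer that the SAP models every visit. No section says so; SAP 7.2 is silent, and 7.2.2 names the four shared visits, though only for summaries. A reader might also infer that the treatment comparison in the text model cannot be estimated. That holds only for the month-1 difference and an average over all five visits. SAP 3.1 refers to change up to 12 months without defining its contrast as such an average, and the continuous-visit fallback and the coded models have no empty cell.

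Finally, the shrinkage is the smaller problem. Even with shared visits only, b2 in Step 2 is 0.038-0.281 against a 12-month effect of 0.5, that is, 44-92% below it, because the code omits the drug-by-month term. That also stands, as a separate matter.

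**Conclusion.** The point holds as a conditional one. The documents contradict each other on whether the trial measured anthropometry at month 1, and the SAP leaves open which visits are modelled. If month-1 heights are in the data and the 10.3 programs run as printed, the single DRUG coefficient is exposed to a schedule-driven distortion: a relative loss of about 9-24% for a linearly growing effect in the four assumed sets (6-33% over the wider grid), and +0.007 to +0.020 Z under no effect with the assumed curved trend. There is no distortion if the effect is constant and the common trend linear. These sizes rest on assumed variances and shapes and on unweighted fits; the weighted program has the same mean model, but the size there was not calculated. A claim that dilution is certain, or that the text model loses its treatment comparison, goes further than the documents allow. The change is still worth making, because it removes a possible bias at almost no cost.

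**What to change.** Reconcile the anthropometry schedule across Protocol Tables 2 and 3 and SAP Table 1. In SAP 7.2, state that only visits scheduled in both cohorts (months 3, 6, 9 and 12, the set already presented in 7.2.2) enter the Objective 2 models, and that any month-1 trial heights are described only. Add the same restriction as a filter in both model programs in SAP 10.3.

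The cost is one sentence and one line per program. The loss is that month-1 treated heights, which have no control counterpart, are not modelled. If no such heights exist, the filter excludes no month-1 data. The change does not resolve the missing drug-by-month term in the code, which needs its own correction.

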9.4. Study size

The determination of study size of this protocol is exclusively limited to addressing the second objective of examining the differences between patients enrolled in the recifercept phase 2 clinical trial and those enrolled in the concurrent external control. For the purposeof consistency with the analysis of the primary endpoint Study C4181005, consideration of study size for this protocol is further limited to a comparison of height growth, defined as the ratio of change from baseline of standing height at 6 months or 12 months of a patient taking recifercept to a matched subject in the concurrent external control. The null hypothesis is the median value (ie, 50 percentile) of the aforementioned ratio is equal to 1.

A table and figure presented below displays the number of pairs required to detect the median ratio (denoted as φ) under the alternative hypothesis (Table 1).

[figure not shown]

Figure 1. Sample Size

9.5. Data management

All data for the described analysis will be obtained from Study C4181001 and Study C4181005 databases. Data management procedures including data collection, retrieval, preparation and retention are described in those protocols.

In summary, for study C4181001 data management involved the completion of a CRF for each study participant. The investigator was responsible for the collection and reporting of all clinical, safety, and laboratory data entered on the CRFs and any other data collection forms (source documents). Additionally, all study data was required to be verifiable by source

PFIZER CONFIDENTIAL CT24-WI-GL02-RF02 3.0 Non-Interventional Study Protocol Template For Secondary Data Collection Study 23-May-2022 Page 21 of 26

documents. Study records were retained by the investigator in accordance with International Council for Harmonisation (ICH), local guidelines, or clinical study agreement (CSA). Records were required to be kept for a minimum of 25 years after study completion or discontinuation of the study or for longer if required by applicable local regulations.

For study C4181005, all participant data relating to the study was recorded on printed or electronic CRF unless transmitted to the sponsor or designee electronically (eg, laboratory data). The investigator was responsible for verifying that data entries were accurate and correct, maintaining accurate documentation of source data that supports the CRF, and ensuring that CRF were securely stored in electronic form. Sponsors or designees were responsible for data management and quality checking the data. Study monitors also performed ongoing source data verification to confirm that entered into the CRF were accurate, complete, and verifiable from source documents. Records and documents pertaining to study conduct were required to be maintained for at least 15 years, unless local policies or institutional regulations required a longer retention period.

9.6. Data analysis

A single pooled dataset will be released for analysis. The release will occur when for selected, targeted data (in Table 3): a) review and documentation of relevant CRF and non-CRF data; and b) all open queries are resolved. There will be two releases of data. The first release coincides with approximately 30 pairs of patients – that is, a patient from C4181001 matched to a patient from C4181005 – having 6 months of growth data. The second release will take place at the beginning of the interim analysis for C4181005. There may be an additional release of data from both studies that coincides with the completion of C4181005.

Descriptive statistics will be tabulated on patient demographic and baseline clinical characteristics between achondroplasia patients from Study C4181005 and patients from Study C4181001 who meet all the inclusion and exclusion criteria of Study C4181005. To construct a concurrent external control for Study C4181005, a propensity score (PS) will be created to achieve balance across covariates between achondroplasia patients from Study C4181005 and patients from Study C4181001 who meet all the eligibility criteria of Study C4181005. The PS will be estimated using standard logistic regression approaches with the "outcome" variable being the data source (whether patients were included in Study C4181005 and exposure to recifercept treatment) and the predictors being the variables associated with both the exposure (recifercept treatment) and the outcomes of interest (i.e. height growth). This model will provide the predicted probability of being in the trial cohort relative to the concurrent external control cohort as a function of the covariates (the propensity score of being included in Study C4181005). The potential covariates may include demographics (e.g. age, gender, race and ethnicity), clinical characteristics (e.g. presence of achondraplasia-related complications, Tanner stage, and other nonachondroplasia-related conditions of medical significance). The distribution of the PS will be reviewed and patients with a PS in the areas of nonoverlap and/or with extreme PS values might be excluded to improve validity (PS trimming). Each patient in the PS trimmed receifercept group will be matched on a ratio of 1:1 with patients in the PS trimmed concurrent external control using optimal nearest neighbour matching with a maximum

PFIZER CONFIDENTIAL

CT24-WI-GL02-RF02 3.0 Non-Interventional Study Protocol Template For Secondary Data Collection Study 23-May-2022 Page 22 of 26

caliper of 1%. Pre- and post-matching balance will be assessed using standardized differences between these two PS-matched groups. A negative control outcome may also be identified to evaluate the pre- and post-matching balance.

After the concurrent external control is constructed by PS matching, descriptive statistics will be tabulated on patient demographic and baseline clinical characteristics between achondroplasia patients from PS-matched recifercept phase 2 trial cohort and those from PS-matched concurrent external control. Two-sample T-tests will be used for continuous variables, and chi-square tests for categorical variables assuming the distribution is normal. Frequency of primary, secondary and exploretary outcomes of interest and 95% confidence intervals will be computed.

Hazard ratios and associated 95% confidence intervals of dichotomous outcomes (including height growth in the achondroplasia reference population +50%, and occurrence of selected achondroplasia-related complications) in PS-matched groups will be estimated by multivariable cox proportional hazards regression models. The effect of recifercept on continuous outcomes (including height growth, anthropometric measures, CCI in PS-matched groups will be estimated by linear mixed

models.

To maximize the number of patients in the trial cohort and the concurrent external control cohort included in this pilot project, additional methods will be explored. Coarsened weighting and full matching may be explored. Other than matching, inverse probability weight (IPW) and/or the fine stratification weighting may also be used to balance the key covariates between patients in the concurrent external control cohort (patients in C4181001 who meet the inclusion and exclusion criteria of Study C4181005) and patients in Study C4181005 (details of these methods will be outlined in the SAP).

